
1. Incidence rate will be calculated for each exposure group as follows:
 $\text{Incidence Rate} = \frac{\sum \text{at risk subjects with at least one event}}{\sum \text{subject years at risk}} \times 100$ 
 
- Incidence rate is defined as the number of 'at-risk' subjects experiencing first event (i.e. number of new cases) during the specified follow-up period divided by total subject-years at-risk of that event for all subjects at risk.
 
- Although the categorization of study follow-up time to Benlysta (Exposed) or Non-Benlysta (Unexposed) depends on the exposure assignment strategy (see Appendix 2, Section 9.2.1 for further discussion), the follow-up time included in the subject-years at-risk calculation, for each month xx time period, starts from enrollment date and ends at the earliest of the following: 
 
o First event date
 
o Last contact date (as defined in Section 9.5.3)
 
o Month xx target date (Section 5.3)
 
o Censored date (for While on Initial Exposure strategy; see Section 9.2.1.1)
 
o Data cut-off date
 
 
Additionally, for some exposure strategies (e.g. 'As-Exposed' strategy; see Appendix 2, Section 9.2.1.2), time to treatment switch and risk windows are also considered when categorizing follow-up time into 'Exposed' and 'Unexposed' period.
 
 
- Calculation of an individual's subject-years at-risk for each exposure strategy is shown in Section 9.2.
 
- Subject-years at-risk will be calculated for each event type separately.
 
- Only the first experience of the event (i.e. new cases) or first primary diagnosis (in the case of a malignant event) which occurred during the 'at-risk' period are counted (see Section 9.2.1 for time period considered for each exposure strategy).
 
- For summary of each specific AESI category, subjects experiencing events in multiple AESI categories will be counted in more than 1 AESI category.
 
 
2. Event rate will be computed for each exposure group as follows:
 $\text{Event rate} = \frac{\sum \text{all AESI events}}{\sum \text{subject years of follow-up}} \times 100$ 
 
- Event rate is estimated for potentially recurrent events and represents the average number of events per unit time of follow-up. It is defined as the total number of events experienced by all subjects during the specified study period divided by subject-years of follow-up. The categorization of study follow-up time depends on the exposure strategy (see Appendix 2, Section 9.2.1). The subject-years of follow-up for each month xx time period takes the same definition above for the subject-years at-risk, however, follow-up does not stop at the time of first event.
 
- Additionally, for some exposure strategies (e.g. 'As-Exposed' strategy), time to treatment switch and risk windows are also considered when categorizing follow-up time into exposed and unexposed period (Section 9.2.1.2)
 
- All events experienced during the follow-up period including recurrent events are counted (see Section 9.2.1 for time period considered for each exposure strategy).
 

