***Benlysta End Date*** + 98 days or 183 days when switching from Benlysta to Non-Benlysta (i.e. Exposed to Unexposed) period. *Period with this end date will be assigned 'Benlysta' or 'Exposed' group.*

***Next Benlysta Start Date*** – 1 when switching from Non-Benlysta to Benlysta (i.e. Unexposed to Exposed) period. *Period with this end date will be assigned 'Non-Benlysta' or 'Unexposed' cohort*
  - For last or final exposure period, ***Period End Date*** is the ***Last Contact Date***\*

- Identify or map events experienced during the study to the specific exposure period satisfying:

Follow-up Period Start Date ≤ Event Onset Date ≤ Follow-up Period End Date

NOTE: for incidence rate calculation, first event is retained for each exposure group (i.e. Benlysta and Non-Benlysta).

- Calculate individual's subject-years of follow-up for time spent in each exposure group *j* (where *j* =1(Exposed), 2(Unexposed)) as follows:

- For overall or 60-Month+ time period, calculate ‘*period follow-up time*’ (*pFUt*) in days for each period  $i$  ( $i=1, 2, \dots, n$ ) as:
  - (Period End Date – Period Start Date) +1
- For other xx-Month time periods ( $xx = 12, 24, 36, 48$ ), calculate ‘*period follow-up time*’ (*pFUt*) in days as follows:
  - Calculate cumulative follow-up duration for each exposure period  $i$  (CM\_FUD[ $i$ ])
  - Identifying qualifying exposure period for each xx-Month time specific computation as period where previous CM\_FUD value is less than xx-Month target visit day (i.e.  $CM\_FUD[i-1] < xx\text{-Month target visit day}$  for  $i=1, 2, \dots, n$ ; where  $CM\_FUD[0] = 0$ )
  - For each qualifying exposure period for xx-Month time, calculate xx-M\_pFUt =
    - $CM\_FUD[i] - CM\_FUD[i-1]$  if  $CM\_FUD[i] \leq xx\text{-Month target visit day}$
    - $xx\text{-Month target visit day} - CM\_FUD[i-1]$  if  $CM\_FUD[i] > xx\text{-Month target visit day}$
    - where  $CM\_FUD[0] = 0$
- Calculate each individual subject-year of follow-up (*syFUj*) as follows:
  - For each exposure group  $j$  ( $j=1$ (Exposed),  $2$ (Unexposed)), sum *pFUt* over all periods  $i$  with the same exposure group and divided by 365.25
    - $syFU_j = (\sum_{i=1}^n pFU_{t_{i(j)}}) / 365.25$  (for overall or 60+Month time period)
    - $xxM\_syFU_j = (\sum_{i=1}^n xxM\_pFU_{t_{i(j)}}) / 365.25$  (for time period specific computation)

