(NOTE: For time period analysis, the above computation will be done for the following time periods: 12-month, 24-month, 36-Month, and 48-Month).

- Individual’s subject-years ‘at-risk’ (*syARj*) will be calculated for each exposure group  $j$  ( $j = 1$ (Exposed),  $2$ (Unexposed)) as follows:
  - Calculate *period ‘at-risk’ time* (*pARTi*) for each exposure period  $i$  ( $i=1, 2, \dots, n$ ) or qualifying exposure period for xx-Month time as:
    - if no event occurred in the exposure period (for overall or 60-Month+ time period calculation) or event day  $> xx\text{-Month target visit day}$  (for xx-Month time period specific calculation)
      - $pART_i = \text{‘period follow-up time’ (pFUt) or}$

$$xxM\_pARt_i = xxM\_pFUt \text{ (for time specific calculation)}$$

- for period where first event occurred (per exposure group) or event day  $\leq$  xx-Month target visit day

$$pARt_i = event\ day - CM\_FUD[i-1]$$

$$xxM\_pARt_i = event\ day - CM\_FUD[i-1] \text{ (in case of time specific calculation)}$$

$$\text{where } CM\_FUD[0] = 0$$

- o For each exposure group  $j$  ( $j=1$ (Exposed),  $2$ (Unexposed)) separately compute individual subject-year at-risk  $syAR_j$  thus:

- For subjects with no events in exposure group  $j$ , sum  $pARt_i$  for all periods  $i(j)$  (i.e. periods occurring while on exposure group  $j$ )

$$syAR_j = (\sum_{i=1}^n pARt_{i(j)})/365.25$$

$$xxM\_syAR_j = (\sum_{i=1}^n xxM\_pARt_{i(j)})/365.25 \text{ (for time period specific computation)}$$

- For subjects with at least one event in exposure group  $j$ , sum  $pARt_i$  for all periods  $i(j)$  up to period where the first event in exposure group  $j$  occurred

$$syAR_j = (\sum_{i=1}^{n^*} pARt_{i(j)})/365.25$$

$$xxM\_syFU_j = (\sum_{i=1}^{n^*} xxM\_pFUt_{i(j)})/365.25 \text{ (for time period specific computation)}$$

where  $n^*$  is the period where the first event was experienced  
(NOTE: Time spent in subsequent exposure periods for the same exposure group after an event had occurred will not be counted)

**NOTE:** Individual's subject-years at-risk will be calculated for each event category separately

\* Last Contact Date as defined in Section 9.5.3

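### SAP 9.2.1.2: the 12- to 48-month As-Exposed at-risk formula for subjects with an event sums follow-up time, so incidence rates would be too low if it is coded as written

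*SAP*

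**What the plan says.** SAP 7.1.5.1 sets up two denominators. The incidence rate is the number of subjects with a first event "divided by total subject-years at-risk of that event for all subjects at risk", and that time ends at the first event if nothing else ends it sooner. The event rate uses follow-up time, which has the same limits; "however, follow-up does not stop at the time of first event".

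SAP 9.2.1.2 turns this into programming hints for the As-Exposed strategy:

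- **Follow-up step.** xxM_pFUt is the length of an exposure period, cut at the xx-Month target day. The event date plays no part. xxM_syFU_j is its sum over all periods in group j, divided by 365.25.
- **At-risk step, by period.** xxM_pARt equals xxM_pFUt if there is no event by the target day, and stops at the event day in the period of the first event.
- **At-risk step, subjects without an event.** xxM_syAR_j is the sum of xxM_pARt.
- **At-risk step, subjects with an event.** The bullet that opens "For subjects with at least one event in exposure group" j says to sum pARt up to the period n* of the first event. The overall (60-Month+) formula does this. The time-period formula beneath it reads "xxM\_syFU_j = (\sum_{i=1}^{n^*} xxM\_pFUt_{i(j)})/365.25".

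A note then adds: "Time spent in subsequent exposure periods for the same exposure group after an event had occurred will not be counted".

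**The concern.** In the last formula both symbols belong to the follow-up step: the result is syFU where syAR is expected, and the summand is pFUt where pARt is expected. It is the follow-up formula with its upper limit changed from n to n*. Read literally, it has two consequences.

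1. No time-period at-risk quantity is defined for subjects with an event. If this sum is used in its place, the rest of the event period after the event, up to the target day, is counted as time at risk. The limit n* and the note remove later periods only.
2. The name xxM_syFU_j already stands for follow-up over all periods. If a program assigns it again here, the event-rate denominator is truncated at n* for these subjects.

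At stake are the As-Exposed tables by time period, 24.210 to 24.212 and 24.310 to 24.312, which include serious infections. Under a constant hazard, the 12- to 48-month incidence rates would fall over time for no real reason, while the overall rate, from the correct formula, would not.

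**Working it through.** **Inputs.** From Protocol 8.2 and Table 8-1: 2,000 and 1,000 patients, 5 years, 10% annual drop-out, and reference rates per 100 patient-years of 5.80 (serious infection), 0.410 (serious psychiatric events), 0.226 (malignancy excluding NMSC, and NMSC) and 0.136 (opportunistic infection). From SAP 5.3: target days 366, 731, 1096 and 1461. Assumed: constant event hazard L and drop-out hazard d = −ln(0.9) = 0.10536 per year.

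**Plan's own figures.** Patient-years = N × (1 − exp(−5d))/d = 7,773.5 for N = 2,000 and 3,886.8 for N = 1,000. Half-width for serious infection = 1.96 × √(0.058/7,773 + 0.058/3,886) = 0.0093 per year, or 0.93 per 100. Both match the protocol, so this set-up is a fair base. The documents give no numeric result for the disputed formula itself.

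**Single subjects.**

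- No switch, first event on day 100. At risk: 100/365.25 = 0.274 years at every time point. As written: 366, 731, 1096 and 1461 days over 365.25 = 1.00, 2.00, 3.00 and 4.00 years.
- Exposed on days 1–500 and 901–1461, first event on day 100, 48-month time point. At risk: 0.274 years. As written: 500/365.25 = 1.369 years. The second exposed period is dropped, but 400 days after the event in the first are kept.

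**Expected rates, no switching.** With T = target day/365.25, mean at-risk time is AR = (1 − exp(−(L + d)T))/(L + d), and mean time as written is FU = (1 − exp(−dT))/d. The rate as written is L × AR/FU. For L = 0.058:

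| Month | AR | FU | AR/FU | Rate as written | Error |
|---|---|---|---|---|---|
| 12 | 0.924 | 0.951 | 0.972 | 5.64 | −2.8% |
| 24 | 1.707 | 1.804 | 0.946 | 5.49 | −5.4% |
| 36 | 2.372 | 2.573 | 0.922 | 5.35 | −7.8% |
| 48 | 2.937 | 3.264 | 0.900 | 5.22 | −10.0% |

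The corrected formula returns 5.80 throughout. Without drop-out the 48-month error is −10.8%. At 48 months the rarer non-fatal events give −0.8% (0.410), −0.4% (0.226) and −0.3% (0.136).

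**With switching.** Simulation of 100,000 patients to 48 months, alternating on and off BENLYSTA from an exposed start, with exponential period lengths (the means are assumptions). Departures of the correct rate from 5.80 are simulation noise.

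| Mean period | Correct | As written | Error | xxM_syFU_j if overwritten |
|---|---|---|---|---|
| 1 year | 5.79 | 5.55 | −4.2% | 2.6% too small |
| 2 years | 5.92 | 5.54 | −6.4% | 1.5% too small |
| 5 years | 5.79 | 5.31 | −8.4% | 0.4% too small |

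**Difference between groups at 48 months.** Assume true rates of 7.0 on BENLYSTA and 5.8 off it, a difference of 1.20.

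- *No switching.* BENLYSTA: AR = (1 − exp(−0.17536 × 4))/0.17536 = 2.875, and 7.0 × 2.875/3.264 = 6.17. NON-BENLYSTA: 5.22. Difference 0.95: it narrows.
- *BENLYSTA exposure ends at hazard 1 per year, no return, and no comparison patient starts BENLYSTA.* BENLYSTA: AR = (1 − exp(−1.17536 × 4))/1.17536 = 0.843, FU = (1 − exp(−1.10536 × 4))/1.10536 = 0.894, and 7.0 × 0.843/0.894 = 6.60. NON-BENLYSTA pools 1,000 comparison patients with the later time of the 2,000: at-risk time is 1,000·A(4) + 2,000·∫₀⁴ exp(−(1 + d)u)·A(4 − u) du, where A(x) = (1 − exp(−(0.058 + d)x))/(0.058 + d). Follow-up is the same with F(x) = (1 − exp(−dx))/d for A. The ratio is 0.909 and the rate 5.27. Difference 1.33: it widens.

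**The case against.** The strongest reply is that the right rule is already in the SAP. The sentence that introduces the formula says to sum pARt, the enclosing step is the computation of at-risk time, xxM_pARt is defined to stop at the event day, and SAP 7.1.5.1 ends at-risk time at the first event. A programmer who follows these gets the right answer, and the code cannot be seen from here. That stands: this is a copy slip with clear intent, and the bias is conditional on the line being coded literally. It does not remove the need to correct the line, because the text is given as programming instruction and a formula is what a programmer is likely to transcribe.

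The reply also limits the scope, and this stands too. SAP 5.1 makes As-Exposed exploratory and Initial Exposure primary, and no hypothesis is tested. The 10.0% is the no-switching case, whereas As-Exposed exists to handle switching; because n* drops later periods, switching shrinks the error.

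A reader might infer three stronger things that the documents do not support:

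- *That the error always narrows a BENLYSTA versus NON-BENLYSTA difference.* It depends on the time left in the event period as well as on the event rate, so it can widen the difference, as shown above.
- *That mortality is affected, at its reference rate of 0.68.* SAP 9.5.3 ends follow-up at death, and SAP 9.2.1 uses the death date for at-risk time, so there is essentially no later time to count.
- *That the time-period and overall rates will visibly clash within one table.* That depends on the layout, and the mock shells are in a separate file.

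**Conclusion.** The formula is wrong as written: it contradicts its own lead-in, the overall formula above it and SAP 7.1.5.1. If coded literally, As-Exposed incidence rates at 12, 24, 36 and 48 months are too low. For serious infections the error grows from 2.8% to 10.0% over those time points with no switching, and is about 4% to 8% at 48 months when mean period lengths of 1 to 5 years are assumed. At the other non-fatal reference rates it is under 1%. No reference rate is given for other infections of interest, so no size can be put on that category. These figures rest on a constant hazard and the protocol's 10% annual drop-out.

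The reused name is a separate and smaller risk. It matters only if the program overwrites the earlier variable, and it would push event rates up, with a denominator 0.4% to 2.6% too small in the simulation.

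The ITT, While On Initial Exposure, Ever-Exposed and weighted analyses do not use this line, and the overall As-Exposed incidence rates are correct. The point should be corrected before the time-period tables are run, but it has no bearing on the primary results.

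**What to change.** In SAP 9.2.1.2, replace the time-period formula for subjects with an event by

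xxM_syAR_j = (sum over i = 1..n* of xxM_pARt_i(j)) / 365.25,

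where n* is the period of the first event in group j on or before the xx-Month target day, or all qualifying periods if there is no such event. Leave xxM_syFU_j as defined in the follow-up step, summed over all periods in group j.

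Then check the time-period program behind tables 24.210 to 24.212 and 24.310 to 24.312. A test subject with a first event on day 100 and no switch should contribute 0.274 years at risk at every time point. SAP 7.2.4 applies the same approach to hospitalization rates, so table 13.310 should be included in the check.

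The cost is one corrected line and one program check. No data, design or primary analysis changes.

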### 9.2.1.3. Ever-Exposed

This exposure strategy accounts for whether a subject was ever-exposed to Benlysta at any point during the follow-up period, once exposed to Benlysta they will always be considered at risk. Any events accrued and all follow-up time after first Benlysta treatment has started will be allocated to Benlysta exposure. Follow-up time before first Benlysta exposure will be allocated to the comparison cohort. Therefore, a subject's exposure group will only change once if a subject moves from a comparison treatment ('Not exposed' onto Benlysta).

A limitation of this strategy is bias from mismatch of events to exposure arm since events occurring after switching off Benlysta are attributed to Benlysta exposure when subjects are no longer exposed.

**Programming Hints for derivation of essential variables needed for computation of incidence and events rates (presented in Section 7.1.5.1) under the ‘Ever-Exposed’ approach:**

- Subjects on Benlysta at enrollment will only have one exposure period (period=1) and Period Start Date = Enrollment Date (as ITT strategy).
- Subjects not on Benlysta at enrollment who do not switch on to Benlysta will only have one exposure period (period=1) and Period Start Date = Enrollment Date (as ITT strategy).
- Subjects not on Benlysta at enrollment who do switch on to Benlysta will have two exposure periods:
  - For period = 1, Period Start Date = Enrollment date, Exposure = Non-Benlysta and Period End Date = Benlysta start date -1
  - For period = 2, Period Start Date = Benlysta start date, Exposure = Benlysta and Period End Date = Last contact date\*.
- Identify or map events experienced during the study to a specific exposure period by checking the event onset within the period start and end interval.

Follow-up Period Start Date ≤ Event Date ≤ Follow-up Period End Date

NOTE: for incidence rate calculation, first event is retained for each exposure group (i.e. Benlysta and Non-Benlysta). This is only applicable for subjects with two exposure periods, i.e. subjects not on Benlysta at enrollment who do switch on to Benlysta.

- Calculate individual’s subject-years of follow-up for time spent in each exposure group as follows:
  - a) Subjects on Benlysta at enrollment:
 
$$\text{Exposed subject-years} = (\text{Last contact date}^* - \text{Enrollment Date} + 1) / 365.25.$$
  - b) Subjects not on Benlysta at enrollment who do not switch on to Benlysta:
 
$$\text{Unexposed subject-years} = (\text{Last contact date}^* - \text{Enrollment Date} + 1) / 365.25.$$
  - c) Subjects not on Benlysta at enrollment who do switch on to Benlysta:
 
$$\text{Unexposed subject-years} = (\text{Benlysta start date} - \text{Enrollment date}) / 365.25$$

$$\text{Exposed subject-years} = (\text{Last contact date}^* - \text{Benlysta start date} + 1) / 365.25$$
- For other xx-Month time periods (xx = 12, 24, 36, 48), calculate period follow-up years as follows:

- a) Subjects on Benlysta at enrollment:  
 Exposed period follow-up years =  $(xx\text{-Month period end date} - \text{Enrollment Date} + 1) / 365.25$ .  
 where  $xx\text{-Month period end date}$  = earliest of  $xx\text{-Month target visit date}$  and  $\text{Last contact date}^*$
- b) Subjects not on Benlysta at enrollment who do not switch on to Benlysta before  $xx\text{-Month target visit date}$ :  
 Unexposed period follow-up years =  $(xx\text{-Month period end data} - \text{Enrollment Date} + 1) / 365.25$ .  
 where  $xx\text{-Month period end data}$  = earliest of  $xx\text{-Month target visit date}$  and  $\text{Last contact date}^*$
- c) Subjects not on Benlysta at enrollment who do switch on to Benlysta before  $xx\text{-Month target visit date}$ :  
 Unexposed period follow-up years =  $(\text{Benlysta start date} - \text{Enrollment date}) / 365.25$   
 Exposed period follow-up years =  $(xx\text{-Month period end date} - \text{Benlysta start date} + 1) / 365.25$   
 where  $xx\text{-Month period end data}$  = earliest of  $xx\text{-Month target visit date}$  and  $\text{Last contact date}^*$
- An individual's subject-years 'at-risk' will be calculated for each exposure group as follows:
 

a) Subjects on Benlysta at enrollment:  
 Exposed subject-years at-risk =  $[(\text{minimum}(\text{Event Date}, \text{Last Contact Date}^*) - \text{Study Enrollment Date}) + 1] / 365.25$

b) Subjects not on Benlysta at enrollment who do not switch on to Benlysta before  $xx\text{-Month target visit date}$ :  
 Unexposed subject-years at-risk =  $[(\text{minimum}(\text{Event Date}, \text{Last Contact Date}^*) - \text{Study Enrollment Date}) + 1] / 365.25$

c) Subjects not on Benlysta at enrollment who do switch on to Benlysta before  $xx\text{-Month target visit date}$ :
 
    - i) If no event happens in period:  
 Unexposed subject-years at-risk =  $(\text{Benlysta start date} - \text{Enrollment Date}) / 365.25$ .  
 Exposed subject-years at-risk =  $(\text{Last contact date}^* - \text{Benlysta start date} + 1) / 365.25$
    - ii) If event happens in period:

Unexposed subject-years at-risk = (minimum (Event date, Benlysta start date) - Enrollment Date)/365.25

Exposed subject-years at-risk =

If Event date  $\geq$  Benlysta start date: (Event date – Benlysta start date+1) /365.25

[figure not shown]
If Event date < Benlysta start date: 0

**NOTE:** An individual's subject-years at-risk will be calculated for each event category separately

\* Last Contact Date as defined in Section 9.5.3

